2.1.2 Cohort 2 Inclusion and Exclusion Eligibility Criteria

Inclusion Criteria

- 2.1.2.1 Age 12 to 26 years
- 2.1.2.2 Females and males
- 2.1.2.3 HIV-positive
- 2.1.2.4 CD4 cell count and HIV-1 RNA level parameters
 - 2.1.2.4.1 CD4 cell count \geq 500 cells/mm³
 - 2.1.2.4.2 HIV-1 RNA level by RT PCR \leq 20,000 copies/ml.
- 2.1.2.5 *Not* receiving antiretroviral treatment with CD4 and viral load parameters as outlined in 2.1.2.4.
- 2.1.2.6 Patients \geq 18 years willing to provide informed consent or parent/guardian willing to provide informed consent for minor children <18 years of age.
- 2.1.2.7 Informed assent for patients 12-17 years of age (Optional at the discretion of the Principal Investigator and Parent/Guardian based on maturity level of minor)
- 2.1.2.8 Willing to use acceptable forms of contraception, if applicable, or abstinence to prevent pregnancy.

Exclusion Criteria

- 2.1.2.9 Any of the following hematologic abnormalities:
 - 2.1.2.9.1 Hemoglobin < 10.0 g/dL
 - 2.1.2.9.2 Neutrophil count < 1500/mm³
 - 2.1.2.9.3 Platelet count < 75,000/mm³
 - 2.1.2.9.4 PT or PTT \geq 1.5X ULN (with the exception of patients with known clotting disorders or known lupus anticoagulant).
- 2.1.2.10 Any of the following hepatic abnormalities
 - 2.1.2.10.1 ALT/SGPT and/or AST/SGOT > 2.5X ULN
 - 2.1.2.10.2 Total bilirubin > 1.5X ULN unless attributable to protease inhibitor therapy.
- 2.1.2.11 Positive tests (antibody and/or antigen) for hepatitis B and hepatitis C viruses, unless the result is consistent with prior vaccination or prior infection with full recovery.
- 2.1.2.12 Acute infection requiring therapy at time of enrollment. Participants may be eligible for study after being on stable and appropriate anti-infective therapy.
- 2.1.2.13 Chemotherapy for active cancer.
- 2.1.2.14 Pregnancy or breastfeeding.
- 2.1.2.15 Use of immunosuppressive or immunomodulating agents within 8 weeks prior to study enrollment. Note: patients receiving oral corticosteroids for management of asthma or contact hypersensitivity for \leq 14 days in duration will be allowed to enroll as long as it has been \geq 30 days since oral corticosteroid administration.
- 2.1.2.16 Known immediate hypersensitivity to yeast or any of the vaccine components.
- 2.1.2.17 Use of investigational agents within 4 weeks prior to study enrollment.
- 2.1.2.18 Active external genital warts requiring treatment or CIN 2/3.

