2.2 RESEARCH ELIGIBILITY EVALUATION

Protocol screening evaluation will be performed within 14 days of starting HPV vaccination and will include a complete history, review of systems and physical examination with documentation of abnormalities.

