3.5.1.2 Laboratory Evaluation

- 3.5.1.2.1 CBC with differential
- 3.5.1.2.2 Acute panel

- 3.5.1.2.3 Hepatic panel
- 3.5.1.2.4 Mineral panel
- 3.5.1.2.5 Serum pregnancy test in post-menarchal females
- 3.5.1.2.6 CD4 percent and absolute cell count

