6.3 PRIMARY VIROLOGIC SAFETY ANALYSIS

Are HIV-1 RNA levels equivalent among HIV-infected patients on HAART versus those not on HAART following vaccination between baseline and timepoint X?

The statistical analysis assumes that an equivalence test will be used, and that no more than 5% of HIV-infected individuals would experience a $\geq 0.5 \log_{10}$ (the range of biologic variation) increase in HIV-1 RNA levels within a week following vaccination or at subsequent time-points. The primary goal of this statistical safety analysis is to determine whether the fraction of patients experiencing a $\geq 0.5 \log_{10}$ increase in HIV-1 RNA levels *at any time within the first week* and up to 1 year following the first immunization, may be considered equivalent between those HIV-infected individuals receiving HAART and those not on HAART following receipt of quadrivalent HPV vaccine. Time-point 1 comparisons of changes in the peak HIV-RNA levels from day 1 between Cohort 1 and 2 during any of the evaluations during the first week (see below) will be considered as the most important primary evaluation for this equivalence study and will be the basis for sample size determination. Another primary evaluation will be based on determining the equivalence of the fractions with day 7 vs. day 1 levels $\geq 0.5 \log_{10}$ (the range of biologic variation) increase in HIV-1 RNA levels between the two cohorts.

Equivalence tests can require a tremendous number of subjects in order to allow only a small interval of difference to be interpreted as equivalent. In order to allow for the test to be done with a moderate number of patients, the two vaccine cohorts will be considered equivalent if the fraction of vaccine recipients in one cohort who have an HIV-1 RNA level increase $\geq 0.5 \log_{10}$ is within 10% of that of the other cohort. Thirty-five patients are required per arm within each HIV-infected cohort, to have 73% power to document this level of equivalence. Formally stated, 35 patients per arm was selected as the sample size in order to allow a single two-group t-test of proportions with a one-sided 0.10 significance level to have 73% power to reject the null hypothesis that the two cohorts are not equivalent with respect to the fraction of patients experiencing a $\geq 0.5 \log_{10}$ increase in HIV-1 RNA levels *at each individual time comparison--the maximum increase within the first week* and up to 1 year following the first immunization.

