Timepoints for HIV-1 RNA Level Analysis: Comparison between Recipients in HIV-Infected Cohorts 1 and 2:

- Timepoint 1 Day 1 vs. Day 3 or Day 7 (immediately s/p vaccination) (*primary*)
- Timepoint 2 Day 1 vs. mos 1 (1mos s/p 1 vaccination)
- Timepoint 3 Day 1 vs. mos 3 (1mos s/p 2 vaccinations)
- Timepoint 4 Day 1 vs. mos 7 (1mos s/p 3 vaccinations)
- Timepoint 5 Day 1 vs. mos 12 (6mos s/p 3 vaccinations)

Within each cohort, the change in \log_{10} HIV-1 RNA levels will be determined between day 1 and day 7 and will be evaluated to see if the values at the two time points are not statistically different from one another. HIV-1 RNA levels below the lower limits of detection (50 copies/ml) will be expressed as 1.69 \log_{10} on a logarithmic scale equivalent to 49 copies/ml. With a minimum of 27 patients in each cohort of HIV-infected individuals, there is at least 95% power to detect a change from day 1 to day 7 with an effect size of 1 SD and a 0.025 two-sided alpha level test (0.05/2cohorts) after allowing for a Bonferroni adjustment.

In addition, as a secondary evaluation, comparison of changes in HIV-1 RNA levels will also be done among the two cohorts from day 1 to day 7, and months 1, 3, 7 and 12 in order to assess if the change in level may have some association with the cohort in which the patient is enrolled. This evaluation will be considered exploratory for all comparisons and timepoints.

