Appendix 2A

Schedule of Study Clinical and Laboratory Evaluations HIV Seropositive Subjects (Cohorts 1 and 2)

	Screening D-14 to D-1	Mo 0 D1	Mo 1	Mo 2	Mo 3	Mo 6	Mo 7	Mo 12
Written Informed Consent	X							
Knowledge & Risk Behavior Survey		X						X
Medical History & Review of Systems	X		X	X	X	X	X	X
Physical Examination	X		X	X	X	X	X	X
Height	X		X	X	X	X	X	X
Weight	X		X	X	X	X	X	X
Vital Signs	X		X	X	X	X	X	X
Chest X-Ray	X							
EKG	X							
Gynecologic Exam/Pap Smear/HPV DNA (Sexually Active Females Only)	X							X
Quadrivalent HPV Vaccine		X		X		X		
VRC Surveillance Report Card to Patient		X		X		X		
Clinical Laboratory Tests:								
CBC with differential	X		X	X	X	X	X	X
PT / PTT	X							
Acute Panel	X		X	X	X	X	X	X
Hepatic Panel	X		X	X	X	X	X	X
Mineral Panel	X		X	X	X	X	X	X
Lipid Panel	X							X
Amylase / Lipase	X							X
Urinalysis	X							X
Serum Pregnancy Test	X		X	X	X	X	X	X
Quantitative IgG & IgG Subclasses	X							X
HIV Serology	X							
Hepatitis B Serology (@ M7 if vaccinated)	X						X	
Hepatitis C Serology	X							
VDRL	X							
CD4 Cell Count (% and Absolute)	X		X	X	X	X	X	X
HIV-1 RNA level	X		X	X	X	X	X	X
HPV DNA Sampling:								
Buccal CytoBrush in PreservCyt (10ml)		X						
Males: Cytobrush® External Genitalia Cytobrush® Anogenital Verge		X						
		X						
Females: Cytobrush® External Genitalia Cytobrush® Anogenital Verge		X						
		X						
Merck HPV Antibody Assay		X					X	X
Research Studies:								
To [name], NCI FCRF: Functional HPV Antibody Assay		X	X		X		X	X
Cryopreserved PBMCs for: HPV/HIV LPA, Cytokine Profiling		X	X		X		X	X
[name] Lab NCI FCRF: Extended FACS		X	X		X		X	X
Serum for Storage		X	X	X	X	X	X	X
[name] Lab: Cryopreserved Whole Blood		X					X	X
[name] Lab: Research Assays Immunologic Responses		X		X		X		

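### Section 6.3 measures every HIV-1 RNA change from Day 1, but no schedule draws HIV-1 RNA on Day 1; the only scheduled pre-dose value is the screening test used for eligibility

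*Combined protocol and SAP*

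**What the plan says.** Section 6.3 lists five HIV-1 RNA timepoints, each measured from Day 1. The primary one is "Timepoint 1 Day 1 vs. Day 3 or Day 7 (immediately s/p vaccination"; the next is "Timepoint 2 Day 1 vs. mos 1 (1mos s/p 1 vaccination", and months 3, 7 and 12 follow the same pattern. The evaluation that section 6.3 ranks as most important compares "changes in the peak HIV-RNA levels from day 1 between Cohort 1 and 2". The within-cohort test is of Day 1 against Day 7, and the exploratory cohort comparison runs "from day 1 to day 7, and months 1, 3, 7 and 12". Section 7.5.1 likewise says that viral replication will be watched through HIV-1 RNA on Days 1, 3 and 7.

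The visit schedules differ:

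- **Section 3.5.1.2 (vaccine visits, months 0, 2 and 6)** lists six laboratory items, the last being "CD4 percent and absolute cell count". HIV-1 RNA is not among them.
- **Appendix 2A**, in the row "HIV-1 RNA level", is marked at Screening (D-14 to D-1), blank at Mo 0 D1, and marked at every visit from Mo 1 to Mo 12. There is no Day 3 or Day 7 column.
- **Appendix 2C** has a 6.0 ml HIV-1 RNA/CD4 tube at Screening and from Mo 1 on, and none at Mo 0 D1.

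The screening sample is the only scheduled pre-dose HIV-1 RNA: "Protocol screening evaluation will be performed within 14 days of starting HPV vaccination". Both HIV-infected cohorts must be at or below 20,000 copies/ml to enter (sections 2.1.1 and 2.1.2).

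**The concern.** An analyst who follows section 6.3 would look for a Day 1 value that the schedule never produces, and would have to substitute one that the plan does not name. The obvious substitute is the screening result. It has passed through a ceiling: among patients whose usual level is near 20,000 copies/ml, those who happened to read low on that day enter and those who happened to read high do not. A later sample from the same patients will be somewhat higher on average with no vaccine effect.

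This affects viremic patients, so it is expected mainly in Cohort 2, which is untreated. Section 8.3 names untreated patients as those in whom vaccine-related upregulation could be more of an issue. The artefact would thus resemble the safety signal being sought, and would differ between the two cohorts being compared.

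**Working it through.** **1. Is the blank cell real?** Tube volumes by column in Appendix 2C:

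- Screening: 3 + 6 + 3 + 4 + 8 = 24 ml (printed 24.0), including the 6 ml HIV-1 RNA/CD4 tube.
- Mo 0 D1: 10 + 60 + 10 + 10 + 18 + 20 = 128 ml (printed 128.0), all from the antibody and research tubes.
- Mo 1: 3 + 6 + 4 + 60 + 10 + 10 = 93 ml (printed 93.0), including the 6 ml tube.

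The Mo 0 total leaves no room for an HIV-1 RNA tube, so the blank is not an artefact of reading the PDF.

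**2. What is missing at each timepoint?** Timepoint 1 lacks its Day 1 reference and also its Day 3 and Day 7 draws. Timepoints 2-5 have their follow-up draws (section 3.5.2.2 and Appendix 2A) and lack only the Day 1 reference. Adding Day 3 and Day 7 alone would leave all five without the stated reference.

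**3. The plan's power figure.** Inputs from section 6.3: 35 per cohort, 5% in each, margin 10 points, one-sided alpha 0.10.

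- SE = sqrt(2 × 0.05 × 0.95 / 35) = 0.0521
- Power = Φ(0.10/0.0521 − 1.282) = Φ(0.638) = 73.8% (73.4% with a noncentral t)

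The stated 73% is reproduced. A Day 1 draw would not change it.

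**4. How large is the drift from a screening baseline?** The documents give no distribution for HIV-1 RNA, so these are assumptions: true log10 level normal with mean 3.3 to 4.3 and between-person SD 0.6 to 0.8; independent within-person variation at each sample; entry if the screening value is at or below log10(20,000) = 4.30; values floored at 1.69 as in section 6.3; no vaccine effect. Within-person SD was set so that two unselected samples give the plan's 5% rate: 0.5/(√2 × 1.645) = 0.215. A larger value of 0.30 was also run.

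| Within-person SD | Rate of rise ≥ 0.5 log10 at one visit, from screening | Same, from a fresh Day 1 value |
|---|---|---|
| 0.215 | about 5.1-6.9% | about 5.0% |
| 0.30 | about 12-17% | about 12% |

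At SD 0.215 the mean upward drift is about 0.01-0.06 log10. The upper end needs a pool centred at 4.3 log10, where half of candidates would fail the ceiling.

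**5. Effect on the equivalence test.** If Cohort 1 stays at 5% and Cohort 2 reads higher only because of its baseline:

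- At 6%: SE = sqrt((0.05 × 0.95 + 0.06 × 0.94)/35) = 0.0545; power = Φ(0.09/0.0545 − 1.282) = 64%.
- At 7%: SE = sqrt((0.05 × 0.95 + 0.07 × 0.93)/35) = 0.0567; power = Φ(0.08/0.0567 − 1.282) = 55%.

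**The case against.** - **A baseline exists.** The opening question of section 6.3 speaks of change from baseline, and an HIV-1 RNA within 14 days before dose 1 is scheduled. This stands in part: it would be wrong to infer that months 1-12 have no pre-dose value at all. But Appendix 2A keeps Screening and Mo 0 D1 in separate columns, and section 6.3 says Day 1 throughout. What is missing is the Day 1 value and a statement of which value serves as baseline.
- **Section 7.5.1 mentions Day 1.** It shows that a Day 1 sample was intended. It is monitoring text and schedules nothing, so it adds to the contradiction and does not resolve it.
- **Timepoint 1 fails anyway.** It drives the sample size and cannot be computed without Day 3 and Day 7. That is correct, and the root cause is shared. The stated primary goal nevertheless extends to one year, and those comparisons lack only Day 1.
- **The bias is small.** This stands. At the plan's own 5% rate it is at most about 2 points on a 10-point margin. At SD 0.30 most of the 12-17% is ordinary variability that a perfect Day 1 baseline would also show. That Cohort 1 is suppressed is also an assumption, since it admits patients up to the same ceiling.
- **CD4 has the same gap.** A reader might infer this, but section 3.5.1.2.6 does list CD4 at month 0. Only Appendices 2A and 2C leave it blank, so it is a conflict between listings.
- **It may be too late.** This version is dated January 2019 and notes that the IND was withdrawn in April 2018. Enrolment status is not stated, so the fix needs a fallback.

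**Conclusion.** The point holds as a contradiction within the protocol: sections 6.3 and 7.5.1 rely on a Day 1 HIV-1 RNA that section 3.5.1.2 and Appendices 2A and 2C do not schedule. The primary virologic safety analysis cannot be carried out as written, whatever the size of any bias.

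The bias from substituting the screening value is small and rests on assumptions outside the documents: a drift of about 0.01-0.06 log10 and a single-visit rate of about 5.1-6.9% against about 5.0% at within-person SD 0.215, or about 12-17% against about 12% at SD 0.30. A reader might infer that the missing draw could hide a vaccine effect on HIV replication. The documents do not support that. The spurious excess is expected mainly in Cohort 2 and points upward, so it makes equivalence harder to show (power of 55-64% instead of 73.8% if Cohort 2 reads 6-7%) or raises a false safety signal. It does not falsely reassure about the untreated cohort.

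**What to change.** 1. Add a pre-dose HIV-1 RNA tube at Mo 0 D1 for Cohorts 1 and 2 in section 3.5.1.2 and in Appendices 2A and 2C.
2. State in section 6.3 that this value is the baseline and that the screening value is for eligibility only.
3. Reconcile section 3.5.1.2 (no HIV-1 RNA) with Appendix 2A (marked) at months 2 and 6. Reconcile the Day 3 and Day 7 samples named in sections 6.3 and 7.5.1 with the visit tables at the same time.
4. Where Month 0 has passed, test stored Month 0 material if it is suitable. Serum and whole blood are kept, but no section plans HIV-1 RNA on them. Otherwise, state in section 6.3 that the baseline is the screening value and report the results with a regression-to-the-mean caveat.
5. Separately, reconcile month 0 CD4 between section 3.5.1.2.6 (listed) and Appendices 2A and 2C (blank). No off-treatment rule needs to change for this.

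The cost of items 1 and 2 is one 6 ml tube and one assay per HIV-infected participant, at a visit where 128 ml is already drawn (128 + 6 = 134 ml), plus text edits. The sample size and the stated power are unchanged.

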5.2 RESPONSE CRITERIA

The primary focus of this clinical study is immunogenicity as measured by development of and change in antibody titers to the four HPV types within the quadrivalent HPV vaccine. HPV-specific antibody titers will be measured at baseline and s/p receipt of 1, 2 and 3 doses of vaccine, in addition to serial, longitudinal monitoring of HPV titers every 6 months following completion of the vaccination series for a total of 4 years to assess antibody titer decay and duration of immunogenicity.

The only clinical outcomes that will be monitored for response are for safety criteria, as this study is not statistically powered to assess vaccine efficacy even on a preliminary level in the currently defined study cohort populations. Safety will be monitored through the use of Vaccination Report Card (VRC) Surveillance for Adverse Vaccine Experiences to assess local injection site and systemic reactions to vaccination, in addition to monitoring of laboratory values. In HIV-infected study subjects, this safety assessment also includes virologic parameters to ensure that HPV VLP vaccination is not associated with upregulation of viral replication and increased HIV-1 RNA levels.

Research assessments that will be evaluated in a descriptive observational manner include:

- Cross-sectional characterization of HPV DNA positivity by oral/buccal and anogenital swabs at baseline in the study cohort populations.
- Longitudinal changes following vaccination in:
 - lymphocyte proliferation assays to HPV and HIV antigens
 - cytokine induction and profile
 - activation and proportional representation of lymphocyte subset populations (HIV-infected patients only)
- Cross-sectional and longitudinal characterization of HPV and HIV knowledge and risk and sexual behaviors in the study cohort populations.

Specific statistical approaches to the primary immunogenicity and virologic safety analyses, and secondary analyses of HIV-related parameters (use of HAART, CD4 cell count and HIV-1 RNA levels) on vaccine immunogenicity are outlined in complete detail in the statistical section 5.4.

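### The within-cohort HIV-1 RNA analysis looks for a non-significant difference with no margin, so it cannot give the assurance of no rise that Section 5.2 asks for

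*Combined protocol and SAP*

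**What the plan says.** Section 5.2 (Response Criteria) gives the purpose. In HIV-infected subjects the safety assessment covers virologic parameters "to ensure that HPV VLP vaccination is not associated with upregulation of viral replication and increased HIV-1 RNA levels".

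Section 6.3 (Primary Virologic Safety Analysis) has two main components.

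- **Between cohorts.** An equivalence test compares the fraction of patients with a rise of at least 0.5 log10 in Cohort 1 (on HAART) and Cohort 2 (no HAART), with a margin of 10 percentage points. It is sized at 35 per cohort and assumes that "no more than 5% of HIV-infected individuals would experience a" rise of that size.
- **Within each cohort.** The day 1 to day 7 change in log10 HIV-1 RNA "will be evaluated to see if the values at the two time points are not statistically different from one another". The support offered is a power statement. It says that "there is at least 95% power to detect a change from day 1 to day 7" when that change is 1 SD. The sample size behind it is 27 per cohort ("With a minimum of 27 patients in each cohort of HIV-infected individuals"), and the level is "a 0.025 two-sided alpha level test (0.05/2cohorts) after allowing for a Bonferroni adjustment".

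For the within-cohort component there is no margin, no confidence-limit rule and no SD in log10 copies/ml.

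**The concern.** For a safety question, the error that matters is concluding that nothing happened when HIV-1 RNA did rise. A difference test controls the opposite error. If the looked-for result is non-significance, fewer patients or noisier measurements make it easier to obtain, and so does a stricter alpha. The Bonferroni step from 0.05 to 0.025 protects against a false alarm and raises the chance of missing a real rise.

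The between-cohort equivalence test does not fill the gap. Both cohorts are vaccinated, and if the vaccine raised HIV-1 RNA to the same degree in each, the difference between them would be zero. The exploratory comparison at the end of 6.3 is also between cohorts. That leaves the within-cohort analysis as the only HIV-1 RNA test in 6.3 that asks whether levels rose after vaccination.

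**Working it through.** **Inputs from Section 6.3:** n = 27 (minimum) or 35 (planned) per cohort; two-sided alpha 0.025; effect size 1 SD. **Assumed:** SD of the within-patient change of 0.3, 0.5 or 0.7 log10. The documents state none. The only indirect guide is the 5% assumption: if changes are normal with mean zero and 5% reach 0.5 log10, then SD = 0.5/1.645 = 0.304.

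**1. The plan's power figure.** For a paired t-test with n = 27, the critical value is t(0.9875, 26) = 2.379 and the noncentrality is 1 × √27 = 5.196. Power is 99.6%, so the stated lower bound of 95% holds. It refers to a change of 1 SD, which is never converted to log10.

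**2. What a non-significant result leaves open.** The largest non-significant observed mean change is t × SD/√n. The 97.5% confidence limit above it is twice that.

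- n = 27: 2.379/5.196 = 0.458 SD; upper limit 0.916 SD.
- n = 35: 2.345/5.916 = 0.396 SD; upper limit 0.793 SD.

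| Assumed SD (log10) | n = 27: observed / upper limit | n = 35: observed / upper limit |
|---|---|---|
| 0.3 | 0.14 / 0.27 | 0.12 / 0.24 |
| 0.5 | 0.23 / 0.46 | 0.20 / 0.40 |
| 0.7 | 0.32 / 0.64 | 0.28 / 0.55 |

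**3. Chance that a true mean rise is non-significant.** This is the noncentral t probability below the critical value, with noncentrality (rise/SD) × √n. For example, a rise of 0.2 at SD 0.5 and n = 27 gives 0.4 × 5.196 = 2.08, and a probability of 60%.

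| True mean rise | n | SD 0.3 | SD 0.5 | SD 0.7 |
|---|---|---|---|---|
| 0.2 log10 (1.6-fold) | 27 | 15% | 60% | 80% |
| 0.2 log10 | 35 | 6% | 49% | 73% |
| 0.3 log10 (2.0-fold) | 27 | 0.4% | 23% | 55% |
| 0.3 log10 | 35 | <0.1% | 12% | 42% |

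**4. The equivalence test does not cover this.** Suppose both cohorts had a true mean rise of 0.30 log10 with normal changes and SD 0.304. The fraction reaching 0.5 log10 would be 1 − Φ((0.5 − 0.30)/0.304) = 25.5% in each cohort instead of 5%. The true difference would still be 0 points, inside the 10-point margin.

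**5. The 0.5 log10 threshold as a margin for the mean.** Requiring the upper 97.5% limit to be below 0.5 would, at n = 27 and SD 0.3, accept an observed mean rise of up to 0.5 − 0.137 = 0.363 log10. The plan's own test would flag anything above 0.137. With a true rise of 0.30 at SD 0.3, the 0.5 rule would declare no relevant rise about 85% of the time, against 0.4% non-significant under the plan. The rule is stricter than the plan only when the SD exceeds 0.5/0.916 = 0.55.

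**The case against.** The best defence is that the test is well powered in its own units: 99.6% for 1 SD at n = 27. If the SD is 0.3 to 0.5 log10, a true mean rise of 0.3 to 0.5 respectively would be missed about 0.4% of the time. If the SD is near the 0.30 implied by the 5% assumption, a rise of 0.3 log10 would almost never be missed. That stands, and it means the size of the problem depends on an SD the plan does not state. It does not make non-significance evidence of no rise: even at SD 0.3, a rise of 0.2 log10 is missed 15% of the time with 27 patients.

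A reader might go further and infer that a rise of 0.27 to 0.46 log10 could be reported as safe. The documents do not support that. Those figures are upper confidence limits at n = 27 under assumed SDs of 0.3 and 0.5; the largest non-significant observed rises are 0.14 and 0.23. A true rise equal to the upper limit would be non-significant only about 1% of the time. Nor do the documents say that a non-significant result will be reported as safe. This test is one of several virologic evaluations, and Section 6.7 adds an accrual stopping rule, although that rule counts individual removals and does not estimate a mean change.

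It could also be said that the point is moot because Appendix 2A has no day 7 sample. The missing sample means the analysis has to be rewritten in any case, and the same logic would fail at whatever visit it was moved to.

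**Conclusion.** The concern holds in a limited form. Section 6.3 seeks a non-significant difference, sets no margin, and leaves Section 5.2's question about a rise after vaccination without a test that could answer it. The between-cohort equivalence test cannot answer it either.

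The part that needs no SD is firm: at n = 27, an observed mean rise of up to 0.46 SD passes as non-significant, with an upper limit of up to 0.92 SD. In log10 units the consequence ranges from minor to serious. A true rise of 0.2 log10 is missed 15% to 80% of the time, and a rise of 0.3 log10 0.4% to 55%, over assumed SDs of 0.3 to 0.7. With all 35 patients the ranges are 6% to 73% and below 0.1% to 42%.

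These figures assume roughly normal changes. That may fit Cohort 1 poorly, because values below 50 copies/ml are all set to 1.69 log10, so a patient undetectable at both visits has a change of exactly zero.

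**What to change.** Do not read non-significance as no change. For each HIV-infected cohort, report the mean within-patient change in log10 HIV-1 RNA with a two-sided 97.5% CI, at the visits where HIV-1 RNA is collected and against a named baseline. State the SD assumed for planning, in log10 units.

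If the report is to say that there was no relevant rise, base that on the upper limit lying below a prespecified margin justified for the cohort mean. Do not borrow the 0.5 log10 value: Section 6.3 uses it for individual patients, and as a margin for a mean it would weaken the check unless the SD were above about 0.55.

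Reconcile the timepoints. Section 6.3 relies on day 1, day 3 and day 7, and Section 7.5.1 also monitors those days. Appendix 2A schedules HIV-1 RNA at screening and months 1, 2, 3, 6, 7 and 12 in the first year, but not at Month 0/Day 1, day 3 or day 7. Section 3.5.1.2 does not list HIV-1 RNA for the month 2 and 6 vaccine visits, so that needs settling too.

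Reporting the estimate and interval costs only wording and uses samples already scheduled, once the baseline is named. Choosing a margin takes more: it needs clinical justification and a power check. As an illustration only, with a margin of 0.3 log10, no true change and a one-sided 0.0125 test, power at n = 27 would be 99.6% at SD 0.304, 77% at SD 0.5 and 45% at SD 0.7; at n = 35 the last two become 88% and 58%.
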